4.1.2. Exclusion Criteria

Patients who meet any of the following criteria will be disqualified from entering the study. Any temporal changes in the following criteria that may prohibit patient consideration, but should normalize for future eligibility, should be reassessed for the patient's future participation in the study:

1. Patients with abnormal coagulation tests during screening, as defined by local laboratory reference ranges, which are not explained by anticoagulant therapy or temporary concomitant affections.
2. Patients with stroke where anticoagulant therapy is contraindicated.
3. Patients with stage 2 hypertension defined as blood pressure confirmed $> 99^{\text{th}}$ percentile + 5 mmHg.
4. Patients with renal function less than 50% of normal for age and size as determined by the National Kidney Disease Education Program version of the Schwartz formula (see Appendix 17.5).⁸
5. Actively bleeding, has a high risk of bleeding, or has a history of major bleeding.
6. Has a currently active gastrointestinal ulceration or a known history of peptic ulcer or gastrointestinal bleeding (including hematemesis, melena, or rectal bleeding including bleeding from hemorrhoids) within the previous 3 months.
7. Has known diabetic retinopathy.
8. Has thrombocytopenia at screening ($< 20 \times 10^9/\text{L}$).
9. Patients with history of major trauma, major or invasive procedures within the last month prior to screening. Otherwise, shorter time may be permitted depending on the surgery and based on the Investigator's judgment of bleeding risk.
10. Patients with known malabsorption disorders (e.g., cystic fibrosis or short bowel syndrome). Otherwise, shorter time may be permitted depending on the surgery and based on the Investigator's judgment.

11. Hepatic disease which is associated with coagulopathy leading to a clinically relevant bleeding risk, alanine transaminase (ALT) > 5 times the upper limit of normal (ULN), or total bilirubin > 2 times the ULN with direct bilirubin > 20% of the total.
12. Patient is currently enrolled in another investigational device or drug study or is receiving other investigational agents. Patients must have completed the prior clinical study at least 30 days prior to dosing.
13. Patients of childbearing potential (post-menarche) who are sexually active and are not using approved contraception, per local practice; who are pregnant (as based on test results); or are breastfeeding.
14. Females with history of abnormal menses, including history of menorrhagia (heavy menstrual bleeding), metrorrhagia, or polymenorrhea.
15. Patient has known hypersensitivity to the active ingredient or any of the excipients of any compounds of the investigational product (IP) (see Appendix 17.1).
16. Positive drug or alcohol screen (excluding cotinine) at screening for patients 12 years of age or older, neonates (0 to 28 days old), and for patients who are being breastfed. Exception to this is if patients are on prescription drug(s). The window to potentially hold and/or resume the prescription drug will need to be determined by DSI based on the information of the prescription drug.
17. Patients who have received a transfusion or any blood products within 30 days prior to the first dose.
18. Patients with any condition that, as judged by the Investigator, would place the patient at increased risk of harm if he/she participated in the study or would interfere with the conduct of the study or the interpretation of the data.
19. Patients with a history of thrombosis who are diagnosed with antiphospholipid syndrome and are triple positive (for lupus anticoagulant, anticardiolipin antibodies, and anti-beta 2-glycoprotein I antibodies).

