Edoxaban is primarily eliminated unchanged in urine and through biliary secretion; with metabolism contributing to a lesser extent towards total clearance of edoxaban. In healthy volunteers, edoxaban is the predominant excreted component in urine, accounting for 24% of the administered dose. In feces, it accounts for 49% of administered dose (Study PRT019). In healthy volunteers, renal and nonrenal clearances contribute equally (approximately 50% each) to the total clearance of edoxaban. The human-specific metabolite, D21-2393, is not detected in urine and only about 2% is detected in feces (A-U139 and PRT019).

In drug interaction studies with P-gp inhibitors (erythromycin, ketoconazole, cyclosporine, and verapamil), exposure of edoxaban increased, but the increase was generally less than 2-fold.

Other drug interaction studies with inhibitors of P-gp and/or other CYPs (quinidine, amiodarone, and dronedarone) also resulted in less than 2-fold increase in edoxaban exposure.

When edoxaban is dosed with a high-fat meal, there is no change in total exposure, but peak exposure increases by about 40%.

Concomitant administration of anti-platelet drugs (aspirin [100 and 325 mg qd \times 5 days] and naproxen [500 mg bid \times 2 days]) was assessed by investigating PK and bleeding times.

Edoxaban exposure was either not affected or minimally affected by concomitant aspirin and naproxen. In all 3 studies, bleeding times increased after administration of edoxaban, but to a lesser extent than those observed with either of the anti-platelet agents alone. Administration of edoxaban in combination with the anti-platelet agents resulted in longer bleeding times than observed for any of the drugs alone. The inter-study comparisons of edoxaban coadministered with either 100 or 325 mg aspirin indicated no significant difference in bleeding times by aspirin dose in these short-term studies. Patients who received edoxaban and aspirin 325 mg had more bleeding adverse events (AEs) than those treated with edoxaban alone or aspirin alone. However, the data are limited and until there is further experience, the dose of aspirin coadministered with edoxaban should be limited to 100 mg in the absence of a compelling indication (e.g., acute myocardial infarction to reduce the risk of bleeding).

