17.5. Modified Schwartz Equation (Pediatric Patients < 12 Years of Age)

$\text{CrCl (mL/min/1.73 m}^2\text{)} = (\text{K} * \text{Ht}) / \text{Scr}$

Height (Ht) in cm; serum creatinine (Scr) in mg/dL

K (proportionality constant): 656

Infant (LBW < 1 year): K = 0.33

Infant (Term < 1 year): K = 0.45

Female Child (< 12 years): K = 0.55

Male Child (< 12 years): K = 0.70

[figure not shown]

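### Renal exclusion 4 and the appendix it cites name different Schwartz equations, and no equation is printed for Cohort 1 (12 to < 18 years)

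*Combined protocol and SAP*

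**What the plan says.** - **Criterion.** Section 4.1.2, exclusion 4, excludes anyone whose kidney function is "less than 50% of normal for age and size as determined by the National Kidney Disease Education Program version of the Schwartz formula", and it refers the site to Appendix 17.5. Inclusion 2 sets the age range from 38 weeks' gestation to under 18 years, so the exclusion applies to all five cohorts.
- **Appendix.** Section 17.5, and its entry in the table of contents, is titled "Modified Schwartz Equation (Pediatric Patients < 12 Years of Age"). It computes creatinine clearance as K × height (cm) / serum creatinine (mg/dL). The constants are "Infant (Term < 1 year): K = 0.45", "Female Child (< 12 years): K = 0.55" and "Male Child (< 12 years): K = 0.70", plus 0.33 for low-birth-weight infants under 1 year. The infant constants do not depend on sex.
- **Not stated.** No section prints an equation or constant for ages 12 to < 18. No section gives reference values for normal or says whether they depend on sex.
- **Background.** Section 1.1.1.5 reports that in healthy volunteers "renal and nonrenal clearances contribute equally (approximately 50% each) to the total clearance of edoxaban". Section 1.3 says the Schwartz equation was used for simulated adolescents but gives no constant. Sections 11.5.1 and 11.10 make 12 to < 18 years the reference cohort.

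**The concern.** Exclusion 4 is the protocol's only numeric renal limit, and it keeps out children who may clear the drug slowly. To apply it a site needs an equation and a normal value. The criterion names one version of the formula, and the appendix it points to prints an equation under another name. The appendix also stops at the age where Cohort 1 begins. For a 12- to 17-year-old the site has a formula by name only. At every age the 50% limit is taken against a normal value that the protocol leaves open.

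Section 6.5 allows no waivers of stated criteria, so compliance has to be verifiable, and here a monitor has no single rule to check against. The sex-specific constants raise a second question: could a boy and a girl with identical measurements fall on opposite sides of the limit, and how much would that matter?

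**Working it through.** The plan gives no figure of its own to reproduce here. The check compares the two places and then works through the printed constants.

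**1. Side by side**

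| Item | Exclusion 4 | Appendix 17.5 |
|---|---|---|
| Equation named | National Kidney Disease Education Program version of Schwartz | Modified Schwartz |
| Ages | All patients, to < 18 years | < 12 years |
| Equation and constants printed | No | Yes, four values of K |
| Normal value printed | No | No |

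**2. Ratio at equal height and creatinine, 1 to < 12 years**

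Boy/girl = 0.70/0.55 = 1.273, so the boy's estimate is 27% higher. This concerns Cohorts 2 and 3 and the part of Cohort 4 aged 1 year or more.

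**3. Example**

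Take 120 cm and 1.2 mg/dL.
- Girl: 0.55 × 120/1.2 = 55.0 mL/min/1.73 m².
- Boy: 0.70 × 120/1.2 = 70.0 mL/min/1.73 m².

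With an assumed common normal of 120 the limit is 60, so the girl is excluded and the boy is not.

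**4. General band**

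Let x = height/creatinine and let N be a normal value common to both sexes (an assumption). The girl is excluded and the boy is not when 0.5N/0.70 ≤ x < 0.5N/0.55.
- The boy's estimate then runs from 50.0% of N to 0.70 × 0.5/0.55 = 63.6% of N.
- The girl's runs from 0.55 × 0.5/0.70 = 39.3% of N to 50.0% of N.

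The documents give no N, so a range is shown:

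| Assumed N | Limit | Band of x | Creatinine limit at 120 cm, girl / boy (mg/dL) |
|---|---|---|---|
| 80 | 40 | 57.1–72.7 | 1.65 / 2.10 |
| 100 | 50 | 71.4–90.9 | 1.32 / 1.68 |
| 120 | 60 | 85.7–109.1 | 1.10 / 1.40 |
| 140 | 70 | 100.0–127.3 | 0.94 / 1.20 |

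**5. What the band is worth in exposure**

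Use the adult split of half renal and half nonrenal, with nonrenal clearance unchanged. Relative clearance is 0.5r + 0.5, where r is renal function as a fraction of normal, and relative AUC is its inverse.
- At the limit, r = 0.50: clearance 0.75, AUC × 1.33.
- A boy just admitted whose value would be 39.3% of normal under the girls' constant, r = 0.393: clearance 0.696, AUC × 1.44.
- Ratio: 0.75/0.696 = 1.08, about 8% extra exposure. This is the most the sex difference can add on this model, and it does not presume that the girls' constant is the right one for boys.

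**6. First birthday**

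For a term infant the estimate at fixed height and creatinine steps up by 0.70/0.45 = 1.56 (boy) or 0.55/0.45 = 1.22 (girl). The limit is relative to normal for age, so this step alone does not show a change in eligibility. It does show that the limit cannot be applied without a stated normal value.

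**The case against.** The best defence is that this is a labelling gap in a workable criterion. Below age 12 the criterion points to one appendix with explicit constants. Above 12 it still names a formula and cites a reference. Screening chemistry includes creatinine, inclusion 8 requires no clinically significant laboratory deviation beyond those of the disease, and exclusion 18 lets the investigator keep out anyone at increased risk. These are real safeguards, and they limit the harm. They do not tell a site which equation to use, or what to compute for a 12- to 17-year-old.

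A reader might infer more than the documents support:
- **That equal renal function passes or fails by sex.** Equal estimates give the same result against a common limit. Estimates differ at equal height and creatinine, and nothing shows that true function is then equal. A sex-specific normal would shrink or remove the effect.
- **That Cohort 1 has no formula.** It has a named one. The equation and constant are missing.
- **That the two versions give different numbers.** The documents show only that the names differ.
- **That the defect costs 33% in AUC.** That is the rise the 50% limit itself permits under the adult split, whichever equation is used.
- **That the constants distort the population model.** No section says Appendix 17.5 feeds it. The one documented Schwartz calculation (Section 1.3) simulated male adolescents, where neither the sex step nor the first-birthday step arises.

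In the text available for this review a figure at the end of Appendix 17.5 is not shown. The age limit stands in the heading and in the table of contents, so the point does not depend on that figure.

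**Conclusion.** The point holds as an inconsistency between a safety exclusion and the appendix it cites. The equation names differ, no equation or constant is printed for ages 12 to < 18, and the normal value is undefined. All three can be read directly from the protocol without assumptions.

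The numerical consequence is modest. The 27% difference between boys and girls at equal height and creatinine is plain arithmetic. A difference in eligibility follows only if the normal value is common to both sexes, and then only in the band described. The 8% ceiling on extra exposure also rests on the healthy-adult renal split. Section 1.1.1.4 says renal function and drug metabolism change with age, so the split may not carry over to children. No analysis result is shown to change. The case for acting is that a safety rule should be applicable and verifiable at every age, and that this one is cheap to repair.

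**What to change.** 1. Reconcile exclusion 4 and Appendix 17.5 so that one stated equation, with its constants, covers every age in the study, including 12 to < 18 years. Which equation governs is for the sponsor to decide.
2. State the reference values behind the 50% limit, and whether they are sex-specific.
3. Once the equation is settled, use it wherever the study calculates creatinine clearance.
4. Check borderline patients already enrolled against the settled rule, from the height and creatinine recorded at screening.

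The cost is a one-page amendment and a short recalculation from data already collected. The downside is that a few patients may change eligibility status and need a note to file.

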4.2. Removal of Patients from Therapy

4.2.1. Reasons for Withdrawal/Early Discontinuation

Any patient who discontinues from the study treatment for any reason will have their study treatment discontinuation recorded. A patient will be considered to have completed the study if they provide the last scheduled PK sample.

Patients may be withdrawn from the study after signing informed consent for the following reasons:

- AE.
- Physician decision.
- Withdrawal of consent by the following:
 - Child,

- Parent, or
- Legal guardian.
- Protocol violation.
- Death.
- Pregnancy.
- Termination of all or part of the study by the Sponsor.
- Other.

If a patient withdraws from the study, the Investigator will complete and report the observations as thoroughly as possible up to the date of withdrawal including the date of treatment and the reason for withdrawal.

If the patient is withdrawn due to an AE, the Investigator will follow the patient until the AE has resolved or stabilized.

All patients who are withdrawn from the study should complete protocol-specified withdrawal procedures (Section 4.2.2).

4.2.2. Withdrawal Procedures

While patients are encouraged to complete all study evaluations, they may withdraw from the study at any time and for any reason without penalty. Every effort will be made to determine why any patient withdraws from the study prematurely. This information should be recorded. All patients who withdraw from the study with an ongoing AE must be followed until the event is resolved or deemed stable. If a patient withdraws prematurely after dosing, all data normally collected prior to study discharge should be collected at the time of premature discontinuation, or at the scheduled end-of-study visit. A genuine effort must be made to determine the reason(s) why a patient fails to return for the necessary visits. If the patient is unreachable by telephone, a registered letter, at the minimum, should be sent to the patient requesting him/her to contact the clinic.

4.2.3. Patient Replacement

Dropouts (for reasons other than AEs) may be replaced, if deemed necessary, upon written approval by the Sponsor. A replacement patient will be within the same age cohort range and will receive the same dose and formulation of IP as the patient being replaced. Any replacements will be made only after receiving the Sponsor's written prior authorization.

4.2.4. Patient Re-screening

Re-screening of patients that fail to meet the Inclusion and Exclusion criteria is allowed if the reason for failure to meet the criteria has resolved and is no longer considered a risk to the patient (e.g., temporal laboratory deviations meeting exclusion criteria, treatment with contraindicated medications, non-chronic diagnoses). Re-screening of patients for this reason will be reviewed on a case-by-case basis and is dependent upon approval from the Medpace and Daiichi Sankyo Medical Monitors. However, if a patient is screened but cannot dose for

personal/logistic reasons within 21 days of screening, they will need to be re-screened. The exception is, patients that were previously on warfarin therapy and need to be within the acceptable range of INR values. This will not be considered rescreening, and only INR values will be monitored at subsequent testing to ensure that prior to edoxaban dosing, the patient meets inclusion with $\text{INR} \leq 2.5$.

5. TREATMENTS ADMINISTERED

5.1. Investigational Products

The Investigator must ensure that the IP will be used only in accordance with the protocol.

According to ICH GCP 1.33, an IP is a pharmaceutical form of an active ingredient or placebo being tested or used as a reference in a clinical study. This includes products with marketing authorizations when used or assembled (formulated or packaged) in a way different from the approved form or when used for an unapproved indication, or when used to gain further information about an approved use.

The IP for this study is edoxaban (DU-176b) in any of the following formulations:

- Edoxaban 30 mg oral tablets.
- Edoxaban granules for oral suspension (60 mg reconstituted with water to provide a 6 mg/mL suspension for oral administration).

Edoxaban doses will be appropriated to achieve exposures comparable to adult doses of 30 mg (low-dose) and 60 mg (high-dose). Patients in the 12 to < 18 years of age cohort will receive multiples of edoxaban tablets of 30 mg strength. Patients < 12 years will receive the liquid oral suspension formulation.

5.1.1. Method of Assigning Patients to Treatments and Blinding

This will be an open-label study. This study is not randomized. Patients will receive edoxaban on 1 occasion. Enrollment will first start in the lower dose group of the oldest age cohort (to achieve exposures comparable to a 30 mg adult dose). After evaluation of PK and safety data from at least half the patients in the lower dose group, enrollment will start in the higher dose group (to achieve exposures comparable to a 60 mg adult dose). If the observed exposures are higher than expected in the lower dose group and exceed the projected 60 mg adult exposure then a lower dose may be investigated in the proposed “high-dose” group. Enrollment in the next younger age cohorts will begin when PK and safety data from at least 50% (N = 6) of patients in the preceding older dose group have been reviewed. Pharmacokinetic and safety data will be reviewed by a DSMB (see Section 11.9) who will approve the start of the next younger age cohort. However, enrollment initiation of Cohort 5 may be considered without PK and safety data from at least 50% of patients in the preceding older dose group. An attempt will be made to enroll patients spanning the entire age range for each age cohort.

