This is a Phase 1, open-label, multiple-center study in pediatric patients from 38 weeks gestation to < 18 years of age. Patients from 5 age cohorts (12 evaluable patients per age cohort) will receive a single dose of edoxaban. Each age cohort will be divided into a low- and high-dose group (6 patients per dose group). Order of enrollment will be from the oldest age cohort to the youngest age cohort. Within each age cohort, enrollment will first start in the lower dose group (to achieve exposures comparable to a 30 mg adult dose). After evaluation of PK and safety data from at least half the patients in the lower dose group, enrollment may then start in the higher dose group (to achieve exposures comparable to a 60 mg adult dose). If the observed exposures are higher than expected in the lower dose group and exceed the projected 60 mg adult exposure, then a lower dose may be investigated in the proposed “high-dose” group. Enrollment in the next younger age cohorts will begin when at least 50% of patients have completed the study in the older age cohort. Enrollment in the younger age cohorts will start only after PK and safety data have been evaluated from at least 6 patients (3 low-dose and 3 high-dose) in the older age cohort. Pharmacokinetic and safety data will be reviewed by a Data and Safety Monitoring Board (see Section 11.9) who will approve the start of the next younger age cohort. However, enrollment initiation of Cohort 5 may be considered without PK and safety data from at least 50% of patients in the preceding older dose group.

Age cohorts and dose groups:

- 12 to < 18 years of age on the day of dosing (12 evaluable total patients)
 - Cohort 1a: Low-dose group (6 patients)
 - Cohort 1b: High-dose group (6 patients)
 - 6 to < 12 years of age on the day of dosing (12 evaluable total patients)
 - Cohort 2a: Low-dose group (6 patients)
 - Cohort 2b: High-dose group (6 patients)
-

-
- 2 to < 6 years of age on the day of dosing (12 evaluable total patients)
 - Cohort 3a: Low-dose group (6 patients)
 - Cohort 3b: High-dose group (6 patients)
 - 6 months to < 2 years of age on the day of dosing (12 evaluable total patients)
 - Cohort 4a: Low-dose group (6 patients)
 - Cohort 4b: High-dose group (6 patients)
 - 38 weeks gestation to < 6 months of age on the day of dosing (12 evaluable total patients)
 - Cohort 5a: Low-dose group (6 patients)
 - Cohort 5b: High-dose group (6 patients)

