3. STUDY DESIGN

3.1. Overall Plan

3.1.1. Study Type

This is a Phase 1, open-label, single-dose, non-randomized, multiple-center PK and PD study in pediatric patients. The study will include 5 pediatric age cohorts with evaluation of 2 different doses within each age cohort (low- and high-dose).

Age cohorts and dose groups:

- 12 to < 18 years of age on the day of dosing (12 evaluable total patients)
 - Cohort 1a: Low-dose group (6 patients)
 - Cohort 1b: High-dose group (6 patients)
- 6 to < 12 years of age on the day of dosing (12 evaluable total patients)
 - Cohort 2a: Low-dose group (6 patients)
 - Cohort 2b: High-dose group (6 patients)
- 2 to < 6 years of age on the day of dosing (12 evaluable total patients)
 - Cohort 3a: Low-dose group (6 patients)
 - Cohort 3b: High-dose group (6 patients)
- 6 months to < 2 years of age on the day of dosing (12 evaluable total patients)
 - Cohort 4a: Low-dose group (6 patients)
 - Cohort 4b: High-dose group (6 patients)
- 38 weeks gestation to < 6 months of age on the day of dosing (12 evaluable total patients)
 - Cohort 5a: Low-dose group (6 patients)
 - Cohort 5b: High-dose group (6 patients)

A total of 60 patients will be enrolled such that 12 evaluable patients will be in each age cohort and 6 patients will be within each dose group. Dropouts or patients with unusable data (for reasons other than AEs) may be replaced.

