3.1.2. Treatment Groups

Patients will be dosed orally with a single dose of edoxaban on Day 1. Patients in the 12 to < 18 years of age cohort will be dosed with multiples of edoxaban tablets of 30 mg strength. Patients younger than 12 years of age will receive the edoxaban granule for oral suspension. The dosing amount and formulation type may change based on emerging data.

If a patient is unable or unwilling to ingest the assigned dosing form (tablet or suspension formulation), the patient will not be enrolled and will be replaced.

Patients will be administered edoxaban in the morning with water.

- Cohorts 1a/1b: 120 mL water;
- Cohorts 2a/2b: 60 mL water;
- Cohorts 3a/3b: 40 mL water;
- Cohorts 4a/4b: 10 mL water;
- Cohorts 5a/5b: 10 mL water.

Patients will be asked to fast for at least 4 hours before dosing and for an additional 2 hours after dosing. If this is not feasible because of the patient's age or other needs, (unflavored) milk, or an equivalent substitute liquid (but not fruit juices), will be allowed until 1 hour before and starting at 1 hour postdose. During this period, the total volume of liquids should not exceed 240 mL, excluding the volume of water utilized for dosing.

Order of enrollment will be from the oldest age cohort to the youngest age cohort. Within each age cohort, enrollment will first start in the lower dose group (to achieve exposures comparable to a 30 mg adult dose). After evaluation of PK and safety data from at least half the patients in the lower dose group, enrollment may then start in the higher dose group (to achieve exposures comparable to a 60 mg adult dose). If the observed exposures are higher than expected in the lower dose group and exceed the projected 60 mg adult exposure, then a lower dose may be investigated in the proposed "high-dose" group. Enrollment in the next younger age cohorts will begin when at least 50% of patients have completed the study in the older age cohort.

Enrollment in the younger age cohorts will start only after PK and safety data have been evaluated from at least 6 patients (3 low-dose and 3 high-dose) in the older age cohort.

Pharmacokinetic and safety data will be reviewed by a DSMB (see Section 11.9) who will approve the start of the next younger age cohort. However, enrollment initiation of Cohort 5 may be considered without PK and safety data from at least 50% of patients in the preceding older dose group.

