In Cohort 1, the oldest age group (12 to < 18 years), doses have been selected on the basis of modeling of adult data to target comparable exposures to 30 mg (low-dose) and 60 mg (high-dose). In this cohort, fixed dosing will be used. In Cohorts 2, 3, 4, and 5, the younger age groups (38 weeks gestation to < 12 years), appropriated doses will be selected to elicit target exposures comparable to those achieved from adult doses of 30 mg (low-dose) or 60 mg (high-dose). Patients in Cohort 1 will receive multiples of edoxaban tablets of 30 mg strength. Patients in Cohorts 2, 3, 4, and 5 will receive the edoxaban granule for oral suspension. The dose that each dose group receives will be determined by Daiichi Sankyo based on emerging PK data and modeled doses needed to achieve target exposures.

Study duration will be approximately 4 weeks for each patient, which will include a screening period (within 21 days of dosing), a treatment period, and a follow-up visit conducted within 10 days after dosing. However, a patient will be considered to have completed the study if they provide the last scheduled PK sample. The treatment period will consist of predose procedures occurring on Day -1 or 1, dosing on Day 1, and postdose procedures occurring postdose on Days 1, 2 (all cohorts) and Day 3 (all patients enrolled prior to Version 5.0 of the protocol may have had Day 3 PK samples obtained). The treatment period days may occur as in-patient or

out-patient based on the clinic's ability/discretion. The overnight stays are not mandatory. Check-out procedures will be performed after the last PK/PD blood samples are collected (Day 2 or Day 3).

An attempt will be made to have a balanced distribution of ages in each age cohort and dose group to provide maximum information regarding PK/PD and safety/tolerability.

In each age cohort, appropriated doses will be selected to target exposures comparable to adult doses of 30 mg (low-dose) or 60 mg (high-dose). This will be done on an ongoing basis, whereby emerging PK concentration-time data from completed patients will be analyzed on an ongoing basis and used to predict the doses required to obtain targeted exposures in upcoming age cohorts and dose groups. Additionally, this ongoing PK analysis will be used to refine and optimize the PK blood sampling scheme (number of samples and timing) in upcoming age cohorts and dose groups.

Refer to the Schedule of Events (Appendix [17.7](#)) and study procedures (Section [6](#)).

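### Section 5.1.1 misstates the gate to the next younger age cohort: its 50% and N = 6 fit the 12-patient age cohort, not the 6-patient dose group it names, and the 3 + 3 dose split is missing

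*Combined protocol and SAP*

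**What the plan says.** The gate to the next younger age cohort appears in three places.

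- **Section 5.1.1** says that enrollment in the next younger cohort begins when "PK and safety data from at least 50% (N = 6) of patients in the preceding older dose group have been reviewed". It gives no split by dose.
- **Section 3.1.2** has two conditions, both set on the older age cohort. One concerns completion: "Enrollment in the next younger age cohorts will begin when at least 50% of patients have completed the study in the older age cohort". The other concerns data: the younger cohorts start "only after PK and safety data have been evaluated from at least 6 patients (3 low-dose and 3 high-dose").
- **The synopsis (Study Design)** carries the same two conditions as Section 3.1.2, including the split. Its data condition begins "Enrollment in the younger age cohorts will start only after PK and safety data have been evaluated".

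Section 3.1.1 gives the sizes: "12 evaluable patients will be in each age cohort and 6 patients will be within each dose group".

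Within a cohort, the high-dose group opens "After evaluation of PK and safety data from at least half the patients in the lower dose group" (Section 5.1.1; Section 3.1.2 and the synopsis agree).

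All three places add that Cohort 5 may be started "without PK and safety data from at least 50% of patients in the preceding older dose group". All three also give the DSMB the decision to start the next younger cohort.

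**The concern.** The percentage, the count and the denominator in Section 5.1.1 cannot all be right. The count and percentage agree with the other two sections. The denominator does not, and the requirement that the 6 patients include 3 at each dose is absent.

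The threshold matters because it decides when younger children are first dosed in what Section 1.2 calls the first pediatric study of the drug. The split is what ensures that high-dose experience in the older cohort has been looked at. Section 6.5 allows no departure from protocol procedures except to remove an immediate hazard, so two different statements of one gate leave it unclear what compliance is.

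The Cohort 5 exception uses the same noun, and it concerns the youngest patients (38 weeks gestation to under 6 months). For the main gate, the synopsis and Section 3.1.2 settle the meaning. For the exception, no copy is worded differently, so nothing in the documents settles it.

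**Working it through.** **Inputs.** Dose group: 6 patients (synopsis; Section 3.1.1). Age cohort: 12 patients (same). Gate in Section 5.1.1: 50%, N = 6, of the older dose group. Gate in Section 3.1.2 and the synopsis: 50% of the older age cohort completed, and 6 patients evaluated, 3 per dose. Step from low to high dose: at least half of the low-dose group.

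**Step 1: try to reproduce N = 6.**

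- On the denominator named, the dose group: 0.50 × 6 = 3, not 6. The stated count is 6/6 = 100% of that group.
- On the age cohort: 0.50 × 12 = 6, and 6/12 = 50%. This reproduces the figure.

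So the count and percentage are sound, and the noun is wrong. If the dose group were kept as the denominator, the count would have to be 3.

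**Step 2: compare with Section 3.1.2.** 3 low-dose + 3 high-dose = 6, which is 6/12 = 50% of the age cohort and 3/6 = 50% of each dose group. The completion condition gives 0.50 × 12 = 6 as well. Section 3.1.2 and the synopsis are consistent within themselves and with each other.

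**Step 3: what Section 5.1.1 could mean if read alone.** The low-dose group comes first, and 0.50 × 6 = 3 of its patients must be evaluated before the high-dose group opens.

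| Reading of Section 5.1.1 | Low-dose | High-dose | Total | Share of cohort |
|---|---|---|---|---|
| A. 50% of the preceding (high-dose) group | 3 | 3 | 6 | 6/12 = 50% |
| B. N = 6 of that group | 3 | 6 | 9 | 9/12 = 75% |
| C. 6 of the age cohort, no split | not stated | not stated | 6 | 6/12 = 50% |

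Under reading C, with low dose enrolled first, the 6 reviewed patients could be 6 + 0, 5 + 1, 4 + 2 or 3 + 3 (low + high). Only 3 + 3 meets Section 3.1.2. Reading A reaches the same result as Section 3.1.2, but ignores the stated N = 6. Reading B keeps N = 6, ignores the stated 50%, and asks for more than Section 3.1.2 does.

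**Step 4: the Cohort 5 exception.** It gives a percentage and no count. On the dose group, what is waived is 0.50 × 6 = 3 of 6 patients. On the age cohort, it is 0.50 × 12 = 6 of 12. The wording is the same in the synopsis and Sections 3.1.2 and 5.1.1, so comparing sections does not help.

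**The case against.** The strongest reply is that this is a slip in one noun with little operational effect. Both numbers in Section 5.1.1 match the rule stated fully, twice, elsewhere. Not repeating the split does not repeal it, since Section 3.1.2 and the synopsis make it a precondition for the whole study. The spread of 6 or 9 patients arises only when Section 5.1.1 is taken in isolation. Nor would a site act on it unaided: the DSMB approves each step to a younger cohort, and the sponsor sets the doses. All of that stands, and it limits the weight of the point. It does not make the sentence correct.

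Two stronger readings are tempting.

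- **A reader might infer that a younger cohort could open with no high-dose patient reviewed.** Section 5.1.1 alone would permit that under reading C. The protocol as a whole does not, because Section 3.1.2 requires 3 high-dose patients and DSMB approval is needed in every version.
- **A reader might infer that the gate lets younger children be dosed before follow-up safety data are seen.** Section 3.1.2 says that "a patient will be considered to have completed the study if they provide the last scheduled PK sample", while the follow-up visit comes within 10 days after dosing (Section 6.4). But completion is only one of the two conditions. Section 3.1.2 separately requires safety data to have been evaluated. Sections 3.1.6 and 11.9 refer the DSMB's work to its Charter, which is not among the documents and may set a data cut-off. A missing cut-off is therefore not established, and this point does not ask for one.

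**Conclusion.** The point holds as a conflict between sections on a safety decision threshold. Section 5.1.1 names a denominator on which 50% is 3, states a count of 6, and omits the 3 + 3 minimum. The intended rule is clear from the synopsis and Section 3.1.2: 6 of the 12 patients in the older age cohort, at least 3 at each dose.

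The size is modest. The count error is 3 against 6 on the denominator named, and the ambiguity is 6 or 9 patients if Section 5.1.1 is read without the rest of the protocol. No safeguard is lost. The conclusion rests only on the group sizes and gate wording in the protocol.

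The Cohort 5 exception is a question and not a finding of error. All three copies name the dose group, so the documents do not show that the age cohort was meant.

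**What to change.** In Section 5.1.1, change the denominator of the gate from *dose group* to *age cohort* and add the split beside the count, so that it reads: at least 50% (N = 6; at least 3 low-dose and 3 high-dose) of the older age cohort. That brings it into line with the synopsis and Section 3.1.2. The change is to wording alone. It adds no patients, tests or waiting time.

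For the Cohort 5 exception, ask the sponsor whether it refers to the dose group (3 of 6) or the age cohort (6 of 12), then word the synopsis and Sections 3.1.2 and 5.1.1 to match. This should not be edited without an answer, because changing the noun could change what is waived for the youngest children.
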